 - Bladder injury, fistula repair or other need for prolonged catheterization
- Sample size
 - A sample size was calculated to be 74 patients in each arm based on the following:
 - The estimated POUR requiring indwelling urinary catheter at 7 days postoperative is 16% (based on internal audit of data)
 - The non-inferiority margin was set at 15%. [11]
 - The power was set at 80%.
 - Due to estimated loss-to-follow-up rate of approximately 13%, the number of patient enrollment was set at 84 subjects in each group, 168 total.
- **Data Collection**
 - Primary outcome:
 - POUR at POD6-8 as defined by need for continued indwelling urinary catheter or intermittent self-catheterization.
 - Continued indwelling urinary catheter will be required in the following settings:
 - Self-removal group – inability to void or sense of incomplete bladder emptying after 5 hours of catheter removal
 - Office-removal group – voided volume less than two-thirds of the instilled volume or PVR greater than 100mL after backfill of up to 300mL

- Secondary outcomes
 - Scores on patient questionnaire collected at the two-week postoperative visit [12,13] (Patient Questionnaire and Visual Analog Scale)
 - Number of patient contact points (office visits, telephone calls and emergency room visits) regarding POUR or indwelling urinary catheter care up to 2 weeks postoperative.
 - PVR measurement at 2-week postoperative visit.
 - UTI diagnosed within 6 weeks postoperative (as defined by positive urine culture, or treatment with antibiotics by a provider).
 - Total duration (number of days) of urinary catheter use (including indwelling urinary catheter and intermittent self catheterization) within 6 weeks postoperative.
- General demographic data
 - Name, date of birth, age, race, weight, height, BMI, parity, tobacco use, medical comorbidities, date of surgery
- Data collection tool
- **Intervention or experimental aspect of the study**
 - Procedure
 - All patients of Cincinnati Urogynecology Associates who undergo vaginal vault suspension (VVS) or robot-assisted laparoscopic sacrocolpopexy (RSCP) will have a backfill VT on POD1 at 6am, per standard practice. The backfill VT will be performed by the nursing staff. Per protocol, up to 300ml sterile saline will be instilled into the bladder and the indwelling urinary catheter will be removed. Patients will be allotted 30 minutes to void. The instilled volume, voided volume, and PVR if needed will be recorded.

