 - Failure of backfill VT is defined by inability to void two-thirds of the instilled volume or PVR greater than 100mL.
 - Patients who fail the backfill VT postoperatively will have an indwelling urinary catheter reinserted and will be taught on its use by nursing staff. They will be approached for possible study enrollment by one of the study investigators.
 - If a patient agrees to participate in the study, she will receive a sealed envelope dictating to which group she will be randomized.
 - All subjects will be provided prescriptions for pain medication, bowel regimen, and cranberry supplements, per standard practice.

- Number of contact points (office visits, emergency room visits, and phone calls to care team) will be recorded during the first two weeks postoperative.
- Self-removal group
 - They will be provided with a diagrammatic handout, illustrating proper removal of their catheter (Diagram for Self-Removal)
 - They will be instructed to remove their indwelling urinary catheter at home on the morning of POD7 at approximately 7am.
 - They will be provided with the phone number of the Research Nurse and the pager number of the on-call staff.
 - On POD6 evening or POD7 morning, the Research Nurse will contact each patient to remind patients of the plan and review proper self-catheter removal.
 - On POD7 they will discontinue their indwelling urinary catheter by way of the instructions provided.
 - If they are UNABLE to void within 5 hours of catheter removal or have feelings of incomplete bladder emptying, they will call the Research Nurse or page the on-call staff. The Research Nurse or on-call staff will arrange a clinic visit for the same day at one of three outpatient clinics (Clifton, West Chester, Kenwood) for replacement of an indwelling urinary catheter.
 - A urine dip will be performed on the urine collected via the catheter. If positive for leukocyte esterase, white blood cells, or nitrites, the urine sample will be sent to the laboratory for culture
 - All urine culture results will be reviewed and if positive, will be treated and recorded. They will return to home with an indwelling urinary catheter and represent to the office for their two-week postoperative visit.
 - If they are ABLE to void within 5 hours of self-removal, they will remain without a catheter and present for their routine two-week postoperative visit the following week.
- Office-removal group

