 - They will call the office to schedule a repeat VT visit on POD6-8 (POD7 will be encouraged).
 - They will have a backfill VT (as described above).
 - If they are UNABLE to void two-thirds of the instilled volume or have a PVR greater than 100ml, they will have an indwelling urinary catheter

reinserted at that time. They will return to home with an indwelling urinary catheter and represent to the office for their routine two-week postoperative visit.

- If they are ABLE to void two-thirds of the instilled volume, they will remain without a catheter and present for their routine two-week postoperative visit the following week.
 - A urine dip will be performed on the foley catheter urine sample prior to the initiation of the backfill VT. If positive for leukocyte esterase, white blood cells, or nitrites, the urine dip will be sent to the laboratory for culture. All urine culture results will be reviewed and if positive, will be treated and recorded.
- Two-week postoperative visit
- All patients will present to the office for routine two-week postoperative visit.
 - Those patients who have an indwelling urinary catheter in place at this time will have a backfill VT performed (as described above).
 - If they are UNABLE to void two-thirds of the instilled volume or have a PVR greater than 100ml, they will either have an indwelling urinary catheter replaced or be taught intermittent self-catheterization. They will have follow-up per standard office practice.
 - If they are ABLE to void two-thirds of the instilled volume, they will remain without a catheter and present for their routine six-week postoperative visit.
 - All patients will have a PVR measured and recorded.
 - All patients will have a urine dip performed (either from a voided urine sample or foley catheter urine sample) at their two-week postoperative visit. If positive for leukocyte esterase, white blood cells, or nitrites, the urine dip will be sent to the laboratory for culture. All urine culture results will be reviewed and if positive, will be treated and recorded.
 - All patients will complete the patient satisfaction questionnaire and VAS at their two-week postoperative visit (Patient Questionnaire and Visual Analog Scale)
 - Six-week postoperative visit All patients will present to the office for routine six-week postoperative visit.
 - All patients will have a urine dip performed at their six-week postoperative visit. If positive for leukocyte esterase, white blood cells, or

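### The primary outcome is actively measured at POD6-8 in the office arm but rests on the woman calling in the self-removal arm, and no rule says how silence or a missed visit is scored

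*Combined protocol and SAP*

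**What the plan says.** Under Data Collection, the primary outcome is "POUR at POD6-8 as defined by need for continued indwelling urinary catheter or intermittent self-catheterization". The settings that count as failure differ by arm:

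- For self-removal it is what the woman herself perceives once 5 hours have passed since the catheter came out: she cannot void, or she feels that she has not emptied.
- For office removal it is measured by staff: "Office-removal group – voided volume less than two-thirds of the instilled volume or PVR greater than 100mL after backfill of up to 300mL"

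Under the Self-removal group heading, on POD6 evening or POD7 morning "the Research Nurse will contact each patient to remind patients of the plan". That is the only scheduled staff contact around POD7, and it comes before the 5-hour window has run. A woman who cannot void, or feels she has not emptied, is to call the Research Nurse or page the on-call staff. For the others the text is "If they are ABLE to void within 5 hours of self-removal, they will remain without a catheter", followed by the routine two-week visit.

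Under the Office-removal group heading, "They will call the office to schedule a repeat VT visit on POD6-8". Staff perform the backfill voiding trial at that visit.

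The Sample size section inflates 74 to 84 in each group for a loss to follow-up of about 13%. The Statistical Analysis section gives an odds ratio with 95% confidence intervals for the primary outcome. Neither section names an analysis set, a missing-data rule, or a coding rule for non-callers and missed visits.

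**The concern.** At POD6-8 two kinds of self-removal woman leave the same record: one who removed the catheter and voided, and one who is silent for another reason (she forgot, could not deflate the balloon, went elsewhere, or felt unwell and did not call). The failure setting, "inability to void or sense of incomplete bladder emptying after 5 hours of catheter removal", also presupposes that removal took place, so a woman who never removed her catheter meets neither the listed failure setting nor the listed success condition. In the office arm a missed voiding trial is visible as a missed trial.

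If silence is read as success, unknown outcomes improve the experimental arm and do nothing for the control arm. In a non-inferiority trial that favours the conclusion the sponsor hopes to reach. The trial is also open to staff and patients, and without a written rule the coding of these women would be settled after their arm is known.

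**Working it through.** **Inputs.** From the Sample size section: POUR rate 16%, margin 15% (taken as an absolute difference), power 80%, 74 per arm, 84 per arm enrolled, loss about 13%. Assumed: the significance level (not stated with the sample size), the share of silent women, and the scoring of silence.

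**Reproducing the plan's sample size.** n per arm = (z₁₋α + z₁₋β)² × [p₁(1−p₁) + p₀(1−p₀)] / margin².

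- One-sided 5%: (1.645 + 0.842)² × (2 × 0.16 × 0.84) / 0.15² = 6.18 × 0.2688 / 0.0225, which rounds up to 74 and matches.
- One-sided 2.5%: (1.960 + 0.842)² × 0.2688 / 0.0225, which rounds up to 94 and does not match.
- Enrolment: 74 × 1.13 = 83.6, which rounds up to 84.

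One-sided 5% is therefore the level implied by the plan's figure and is used as the main case. One-sided 2.5%, which corresponds to a two-sided 95% interval, is shown beside it.

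**Scenario.** Self-removal is truly worse by exactly the margin: 16% + 15% = 31%, against 16%. A share L of women in each arm gives no POD6-8 information. In the self-removal arm they are scored free of POUR, so 84 are analysed with an apparent rate of 0.31 × (1 − L). In the office arm they drop out, leaving 84 × (1 − L) at 16%. Non-inferiority is declared when the upper Wald bound of the risk difference is below 0.15. The probability is an exact sum over both binomial distributions.

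| Silent share L | Office n | Apparent self-removal rate | False non-inferiority, one-sided 5% | One-sided 2.5% |
|---|---|---|---|---|
| 0% | 84 | 31.0% | 5.2% | 2.6% |
| 5% | 80 | 0.31 × 0.95 = 29.5% | 8.3% | 4.5% |
| 13% | 73 | 0.31 × 0.87 = 27.0% | 14.5% | 9.3% |
| 20% | 67 | 0.31 × 0.80 = 24.8% | 23.4% | 17.6% |
| 30% | 59 | 0.31 × 0.70 = 21.7% | 41.0% | 31.5% |

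**Comparison: symmetric handling.** With 13% missing in both arms (73 against 73, true rates 31% and 16%), false non-inferiority is 5.3% at one-sided 5% and 2.7% at one-sided 2.5%.

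**No loss is needed.** With 74 per arm and nobody lost, if 13% of true self-removal failures simply do not call, the apparent rate is again 27.0% and false non-inferiority is 15.1% at one-sided 5%.

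**The case against.** A reader might infer that the protocol defines success in the self-removal arm as the absence of a call, that women who are lost or never remove the catheter are scored free of POUR, and that an office no-show is missing. The documents do not say any of this:

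- Success is a positive condition, being able to void within 5 hours of self-removal. A woman who kept her catheter does not meet it.
- The primary outcome is the need for a continued catheter, so a retained catheter could be read as POUR, in either arm.
- The inflation to 84 is applied to each group, which suggests that losses are expected to drop out of both.

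There are later checks. At two weeks a catheter still in place is seen and tested, and PVR is measured in all women. Office, emergency room and telephone contacts are recorded for two weeks, and catheter days are extracted from the chart at six weeks. A data collection tool is named but its contents are not visible, so one cannot say what the forms omit.

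The calculation is also conditional. The 13% is a general loss allowance, not a rate of silence on POD7, and the test is on the risk difference while the plan names an odds ratio.

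Most of this stands, and it limits the point to a risk rather than a fixed scoring error. It does not remove the point. None of the later checks is linked to the primary outcome. The two-week visit helps only if the woman attends, and the chart holds a home removal date only if someone obtains it. That a retained catheter can be read in two ways is itself a reason to write the rule down.

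**Conclusion.** The point holds as a cheap improvement. Followed as written, the plan ascertains the primary outcome actively in one arm and passively in the other, and gives no rule for non-callers, unremoved catheters or missed visits. Silence may then be counted as free of POUR in the self-removal arm only, and the resulting bias would run towards non-inferiority.

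The size depends on an assumed share of silent women and on that scoring being adopted. At one-sided 5%, false non-inferiority goes from about 5% to 8.3% with 5% silent and 14.5% with 13% silent; it stays at about 5.3% if losses are missing in both arms. These figures illustrate what a written rule protects against. They are not error rates of the plan itself.

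It is also tempting to say that a catheter taken out by staff should count as a primary-outcome failure. The documents do not support that: a woman who is catheter-free and voiding does not have POUR under the stated definition, and counting her as a failure would change the endpoint.

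**What to change.** 1. After the 5-hour window, record for every self-removal woman whether, when and by whom the catheter was removed, whether she voided, and whether any catheter has been placed since. The Research Nurse, who already contacts each woman beforehand, can do this by call on POD7-8; at the latest it can be a fixed question at the two-week visit.
2. Score non-POUR only when a catheter-free state with voiding is confirmed. In the office arm the voiding trial already supplies this.
3. Write one rule, identical in both arms, for a catheter still in place at the end of POD8, and treat unknown outcomes as missing in both arms.
4. Add a sensitivity analysis counting unknowns as POUR. Applied to both arms it pulls the difference inwards: with 13% unknown, 0.31 × 0.87 + 0.13 = 40.0% against 0.16 × 0.87 + 0.13 = 26.9%, and false non-inferiority is 8.4% at one-sided 5%. It should therefore not be presented as conservative on its own; a version counting unknowns as POUR in the self-removal arm only would be.
5. Report failed self-removal separately as a descriptive result, outside the primary outcome, and exclude the scheduled call from the contact-point count.

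The cost is protocol and form wording plus one short call per self-removal woman. The call gives that arm slightly more attention and could affect satisfaction scores, which is avoided if the question is asked at the two-week visit. The observed self-removal rate may come out less favourable.

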Date	7-26-2018
Title	Is Self-discontinuation of a transurethral catheter following pelvic reconstructive surgery as effective as office-based discontinuation?; A Randomized Controlled Trial
Principal Investigator	[name]
Sub-Investigators	[name]; [name]; [name] MSc; [name], DO; [name], [name]
Research Specialist	[name], MS
Department	Department of OB/Gyn, Division of Urogynecology and Reconstructive Pelvic Surgery
Hatton #	16-075

Purpose of Study:

- To determine if self-discontinuation of transurethral foley catheters in patients diagnosed with postoperative urinary retention (POUR) following inpatient pelvic organ prolapse surgery is non-inferior to office-discontinuation.
 - **Primary Aim:** To determine the incidence of POUR (as defined as the continued need for catheterization) at postoperative day 6-8 (POD6-8) following inpatient pelvic organ prolapse surgery in patients who self-discontinue their indwelling urinary catheter compared to those who present to the office for discontinuation.
 - **Secondary Aims:** To compare patient satisfaction, number of patient related encounters (emergency room, office visit, or telephone calls), incidence of postoperative urinary tract infection (UTI), post void residual volume (PVR) at 2-week postoperative visit, and total duration of catheter use between the two groups.

Hypothesis or Research Question

- We hypothesize that self-removal of indwelling urinary catheters will be non-inferior to office-removal on POD6-8 regarding ongoing symptoms of POUR following inpatient pelvic organ prolapse surgery.
- We further hypothesize that self-removal of indwelling urinary catheters will result in fewer office visits and improved patient satisfaction in the immediate postoperative period.
- In addition, we hypothesize that the duration of POUR (number of days urinary catheter use is required) will be equivalent in the self-removal group compared to that of the office-removal group.
- Lastly, we hypothesize that there will be less incidence of UTI in the self-removal group.

Background

Postoperative urinary retention (POUR) is a common issue following urogynecologic surgery, with incidence rates of 1.4-43% [1-5]. The wide range of incidence is due to the lack of a

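### Only the office arm has every patient's urine tested at POD6-8, so the planned UTI comparison alone cannot show that self-removal lowers UTI incidence

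*Combined protocol and SAP*

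**What the plan says.** All references are to the combined protocol and SAP.

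- **Outcome** (Data Collection, Secondary outcomes): "UTI diagnosed within 6 weeks postoperative (as defined by positive urine culture, or treatment with antibiotics by a provider"). There is no symptom criterion.
- **Hypothesis** (Hypothesis or Research Question): "we hypothesize that there will be less incidence of UTI in the self-removal group".
- **Before randomization** (Intervention, Procedure): every patient "will have a backfill VT on POD1 at 6am, per standard practice".
- **Office-removal group, POD6-8**: "A urine dip will be performed on the foley catheter urine sample prior to the initiation of the backfill VT". A dip positive for leukocyte esterase, white cells or nitrites goes to culture, and positive cultures are treated and recorded.
- **Self-removal group, POD7**: under the same-day clinic visit for catheter replacement, "A urine dip will be performed on the urine collected via the catheter". For the others, "If they are ABLE to void within 5 hours of self-removal, they will remain without a catheter" and their next scheduled visit is at two weeks.
- **Two weeks, both arms**: "All patients will have a urine dip performed (either from a voided urine sample or foley catheter urine sample) at their two-week postoperative visit".
- **Six weeks, both arms**: "All patients will have a urine dip performed at their six-week postoperative visit".
- **Statistical Analysis**: categorical variables are compared by Fisher's exact or Pearson chi-square tests. Nothing separates UTIs by how they were found.

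**The concern.** With no symptom criterion, a culture prompted by a routine dip in a patient without complaints counts as a UTI. The scheduled dips differ between arms by one: the office arm has the POD6-8 dip in everyone, and the self-removal arm has it only in patients who come back. The arm with more testing will tend to record more UTIs even if infection is equally common.

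The protocol predicts fewer UTIs with self-removal, so this difference in testing works in favour of the hypothesis. A significant result could be reported as an infection benefit of self-removal when some or all of it came from unequal testing.

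**Working it through.** **1. Timing of the extra dip.** The office sample is taken before the POD6-8 backfill, and the POD1 backfill is common to both arms. A positive on that dip therefore arose before the removal method could act and cannot have been caused by the POD6-8 backfill.

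**2. Direction.** UTI is scored ever/never. An extra dip can move a patient from not counted to counted. It cannot do the reverse, since a patient treated for a positive culture has already been counted.

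**3. Inputs from the documents.** The plan gives no UTI figure to reproduce. The sample size, set for retention, reproduces with a one-sided 5% test (alpha is not stated): (1.645 + 0.842)² × 2 × 0.16 × 0.84 / 0.15² = 73.9, giving 74 per arm, and 74 × 1.13 = 83.6, giving 84. After 13% loss, 84 × 0.87 = 73 per arm, used below. The share of the self-removal arm dipped at POD7 is r = 0.16, taking the audited retention rate as a proxy.

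**4. Assumptions.** These are not in the documents. All are equal in truth between arms.
- u = background UTI rate from everything except the POD6-8 dip: 15%, range 5-25%
- d = POD6-8 positive rate: 5-30%
- s = share of missed self-removal positives recorded later anyway: 0-100%

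**5. Recorded rates.**

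Office = 1 − (1 − u)(1 − d)

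Self-removal = 1 − (1 − u)(1 − d[r + (1 − r)s])

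With u = 0.15 and d = 0.20:
- Office: 1 − 0.85 × 0.80 = 32.0%
- Self-removal, s = 50%: the bracket is 0.16 + 0.84 × 0.5 = 0.58, so 1 − 0.85 × (1 − 0.116) = 24.9%
- Self-removal, s = 80%: the bracket is 0.832, so 1 − 0.85 × (1 − 0.1664) = 29.1%

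With d = 0.05: office 19.2%; self-removal 17.5% (s = 50%) or 18.5% (s = 80%).

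**6. Chance of a false finding of significantly fewer UTIs with self-removal.** Exact enumeration of two binomials, 73 per arm, two-sided 5%, u = 15%. The chi-square nominal rate in this direction is 2.5%; Fisher's test actually runs at about 1.6%.

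| s | Test | d = 5% | 10% | 20% | 30% |
|---|---|---|---|---|---|
| 0 (extreme bound) | chi-square | 8% | 19% | 52% | 82% |
| 50% | chi-square | 5% | 7% | 16% | 27% |
| 80% | chi-square | 3% | 4% | 6% | 8% |
| 100% | chi-square | 2.5% | 2.4% | 2.5% | 2.6% |
| 50% | Fisher | 3% | 5% | 12% | 22% |
| 80% | Fisher | 2% | 3% | 4% | 6% |

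Over u = 5-25% and d = 5-30%, the chi-square range is 4-37% at s = 50% and 3-9% at s = 80%.

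**7. Sensitivity to the return share.** At u = 15% and d = 20%, moving r from 5% to 31% (16% plus the 15-point margin) takes the chi-square figure from 19% to 12% at s = 50%, and from 6% to 5% at s = 80%.

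**8. Check on a symptom-triggered definition.** This has a bias of its own, because office-arm positives found at POD6-8 are treated while those missed in the self-removal arm are not. Let b be the symptomatic UTI rate otherwise and k the share of missed positives that become symptomatic. Then office = b and self-removal = 1 − (1 − b)(1 − 0.84dk). With b = 8% and d = 20%, office is 8.0% and self-removal is 9.5% (k = 10%) or 11.9% (k = 25%). A false result against self-removal then occurs in about 5% or 12% of trials. Over b = 4-12%, d = 5-30% and k = 10-25%, the range is 3-31%.

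**The case against.** The strongest counter-argument is that the office visit and its dip belong to the strategy being randomized. The outcome is worded as UTI diagnosed, and as a count of diagnoses under each pathway it is valid. That stands. It does not cover the hypothesis, which is worded as incidence.

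Second, both arms are dipped again about a week later and at six weeks, so most missed positives might be recorded anyway. At s = 90% the false-positive rate is only 2.8-4.9% over u = 5-25% and d = 5-30%. This also stands as a limit on size. Nothing in the documents assures complete later capture, however: an untreated positive may clear before two weeks, and the two-week sample may be voided rather than catheter urine.

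Third, self-removal patients have a reminder contact from the Research Nurse and telephone and pager access, which might lead to antibiotics and offset the bias. If this added a 2% chance of a recorded UTI, the false-positive rate would fall to 2.6% (d = 5%, s = 50%) or 2.3% (d = 10%, s = 80%), but would still be 4.6% at d = 10%, s = 50%. The 2% is an assumption applied to one arm only, and office patients have a face-to-face visit at which the same could happen. The calls the protocol describes lead to the clinic visit whose dip is already included through r.

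Finally, the symptom-triggered analysis is itself biased, as step 8 shows. That is why it can be only a sensitivity analysis.

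**Conclusion.** The concern holds. The direction of the extra dip's effect follows from the text: with equal true rates it can only raise the recorded office-arm count. The planned test cannot separate that from a real difference, so on its own it cannot support a claim of lower UTI incidence with self-removal.

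The size is unknown. It ranges from no bias, if every missed positive is recorded later, to a substantial false-positive rate if about half are. It depends on the assumed background, POD6-8 positive rate and later capture. UTI is a secondary outcome with no power calculation, and the primary retention comparison is not affected. The point should be addressed because the correction is cheap and the plan states a directional claim.

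**What to change.** 1. For each positive culture or antibiotic course, record whether a protocol dip (and at which visit) or symptoms triggered it. Take this from the chart for participants who have finished follow-up.
2. Report UTI under the planned definition and show separately, by arm, the UTIs whose only evidence is the POD6-8 protocol dip.
3. Add a sensitivity analysis limited to symptom-triggered cultures and treatment. State that treating office-arm screen positives can bias it against self-removal, and that unblinded symptom reporting can bias it either way. Do not present the two definitions as bracketing the truth, and do not replace the planned one.
4. Describe the main result as UTIs diagnosed or treated under each pathway. Do not conclude from it alone that self-removal reduces UTI incidence.

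The dips and their treatment stay as they are.

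The cost is one data field, some chart abstraction and one sentence limiting the claim; chart extraction is already planned for catheter days. Charts may not always show why a culture was sent, and the sensitivity analysis will have fewer events. A new prospective symptom question is not proposed. From 1/01/2017, adding 4 + 2 + 6 = 12 weeks of preparation and 18 months of collection gives about 26 September 2018, against a document dated 7-26-2018. If the 2017 date already marks the start of collection, it would end about 1 July 2018 and the abstraction might be wholly retrospective. Actual accrual is not given.
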